6.3.2 Attribution of the AE

The investigator or co-investigator is responsible for assignment of attribution. Definite – The AE is clearly related to the study treatment/intervention. Probable – The AE is likely related to the study treatment/intervention. Possible – The AE may be related to the study treatment/intervention. Unlikely – The AE is doubtfully related to the study treatment/intervention. Unrelated – The AE is clearly NOT related to the study treatment/intervention.

6.4 Serious Adverse Event Reporting Guidelines

The PI must be notified within ONE business day of study team's knowledge of any event meeting the criteria and definition of a serious adverse event, regardless of attribution, occurring during the study or within 30 days of the last administration of the study related treatment/intervention.

The investigator must report all events meeting the criteria and definition of a serious adverse event as per the IRBMED reporting guidelines.

6.5 Other Reportable Information or Occurrence (ORIO)

There are types of incidents, experiences, and outcomes that occur during the conduct of human subject research that represent unanticipated problems but are not considered adverse events. For example, some unanticipated problems involve social or economic harm instead of the physical or psychological harm associated with adverse events. In other cases, unanticipated problems place subjects or others at increased risk of harm, but no harm occurs.

Unanticipated problem: Per FDA Procedural Guidance for Clinical Investigators, Sponsors, and IRBs (January 2009), an unanticipated problem is defined as a serious problem that has implications for the conduct of the study (requiring a significant and usually safety-related, change in the protocol (such as revising inclusion/exclusion criteria or including a new monitoring requirement), informed consent or investigator's brochure).

Upon becoming aware of any incident, experience, or outcome (not related to an adverse event) that may represent an ORIO, the investigator should assess the incident and follow IRBMED's reporting guidelines.

6.6 Unblinding Procedures

In the event of any adverse event requiring unblinding, the study staff can be made immediately aware of intervention assignment and the PI will be notified.

7.0 STATISTICAL CONSIDERATIONS

Aim 1 - Acceptability and Tolerability. Neuromodulation studies typically use dropout rate and reported adverse events as measures of acceptability and tolerability, respectively.¹² We will compare the percentage of participants requesting to discontinue the session and the severity of side effects reported following the tACS vs. sham procedure using Bayes factors (BF).

Aim 2 - tACS Effects on Neural Synchrony and Cognitive Control Behavior. EEG data preprocessing and spectral analyses will be conducted using custom MATLAB scripts and EEGLAB following the general methods described in **PI [name]**'s published work.⁷ Briefly, data will be downsampled to 500 Hz, filtered (0.1 – 100 Hz), re-referenced to common average, segmented into short epochs (for task data, -400 to 1800 ms time-locked to onset of stimuli; for rest data, 2 s epochs), applied independent component analysis to reject non-neural artifacts, baseline adjusted, followed by automatic artifact rejection of epochs containing voltage exceeding ±100 μ V. Data will be mirrored on both ends to minimize edge artifacts, applied Morlet wavelet convolution to extract power of different frequencies from 2 to 60 Hz. Theta-gamma PAC will be computed using the Kullback-Leibler Modulation Index (KLMI)⁸ implemented in the PAC Tools plugin for EEGLAB.⁹ Neural synchrony (theta-gamma PAC) during the rest EEG blocks and cognitive control performance (sensitivity d', response bias β , and reaction time on the Emotion Go-NoGo task) will be analyzed in separate repeated-measures ANCOVAs, with stimulation (tACS, sham) as within-subjects factor.

Potential Problems & Alternative Strategies

Participants Dropout. The study design entails each participant completing all 3 sessions. Our experience of conducting multiple-session neuromodulation studies suggests that average dropout rate for each subsequent session is 10-15%. We will enroll 30 participants to ensure that at least 20 participants will complete the study even with an overall dropout of 30%.

Statistical Power. For the repeated-measures ANOVAs in Aim 2, assuming a conservative withinsubjects correlations of 0.8, a sample size of 20 would provide 80% power at alpha level of .05 to detect small-to-medium within-subjects effect sizes of f=0.21. Although N = 20 may not be sufficient to detect smaller effects, our findings will still be useful in providing effect size estimates aiding the sample size calculations for subsequent clinical trials. Additionally, we will use Bayesian methods described in [name] publication¹⁵ to estimate the posterior probabilities of beneficial tACS effects. Although the sample will be small, we will also analyze for effects of sex, as the expectation is that we will have 50:50 distribution of male:female.

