2.0 STUDY DESIGN, AIMS AND OUTCOME MEASURES

The randomized, double-blind, sham-controlled, cross-over study will involve three sessions. The first session will involve a clinical interview, questionnaires, and EEG recording during a computerized task. The second and third sessions will involve tACS brain stimulation (or placebo stimulation) during a computerized task and EEG recording. Participant's psychiatric phenotypes and functioning will be dimensionally characterized. Affective cognitive control in bipolar disorder will be assessed using the Emotion Go-NoGo Task.

Aim #1: Evaluate the feasibility and acceptance of tACS among bipolar patients. Neuromodulation studies typically use dropout rate and reported adverse events as measures of acceptability and tolerability, respectively¹⁰. We will compare the percentage of participants requesting to discontinue the session and the severity of side effects reported following the tACS vs. sham procedure using Bayes factors (BF).

Intervention: One-session tACS

Primary outcome measure 1: Severity of side effects reported at end of stimulation session. This is calculated by summing the severity score of items (0-4) that are rated by the participant as related to stimulation (ratings of 3=probable or 4=definite) on the Stimulation Side Effects Questionnaire. **Primary outcome measure 2**: Withdrawal during or after the stimulation session.

Aim #2: Estimate the preliminary effects of personalized tACS on theta-gamma phase-amplitude coupling (PAC) and cognitive control behavior in BD.

Intervention: One-session tACS

Primary outcome measure 3: Accuracy signal detection theory metric sensitivity (d') derived from the behavioral responses to Go and NoGo trials on the cognitive control task.

Primary outcome measure 4: Accuracy signal detection theory metric response bias (β) derived from the behavioral responses to Go and NoGo trials on the cognitive control task.

Primary outcome measure 5: Reaction time (millisecond) of Go trials on the cognitive control task. **Primary outcome measure 6**: Theta-gamma PAC (Kullback-Leibler Modulation Index) during the rest EEG blocks interleaved between stimulation blocks.

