Flanker Task. After completing the Emotion Go-NoGo task, participants will perform a separate cognitive control task (i.e., Flanker task; described below). Accuracy and reaction time will be used to index cognitive control behavior as outcome measures. EEG recorded during the Flanker task will be used to assess neurological indicators of attention control. Participants will then be 50-50 randomized to receive either the Sham treatment first or tACS treatment first at Session 2.

7) Randomization. Subjects will be randomized on a 50-50 basis to receive active vs. sham stimulation. If participants are randomized to the active group at Session 2, they will go to the sham group at Session 3, and vice versa. The participant will not be told which group they were randomized to. The randomization schedule will ensure an equal distribution across the group. Randomization lists

will be generated by random condition generator and will be programmed into the computer that controls the tACS device by the postdoc fellow or PI.

Sessions 2 and 3: Sham vs. Active tACS Session (~2-3 hours)

These sessions will occur at the University of Michigan Rachel Upjohn Building. Participants will undergo two sessions, separated by ~ 1 week. Procedures will be identical for each session.

- 1) *Pre-Visit Preparations*. Research staff will contact the participant to remind them about the study visit and to ask if they have had any medication changes since their last visit. If yes, the participant will be re-scheduled for an appointment time in which the criteria for a stable dose of at least two weeks has been achieved. Additionally, participants will also be asked if they have had any recreational drug use since their last study visit. If yes, the participant will have to be re-scheduled 30 days out.
- 2) *Arrival on scheduled session day*. Participants will arrive at the Rachel Upjohn Building where they will be greeted by a member of research staff and escorted to the treatment room. Pregnancy urine test will be given if participant opted out of signing the Pregnancy Attestation Form.
- 3) *Clinician Administered Assessments*. In-person clinical assessments will be completed by a trained member of staff. All study clinicians are blinded to the treatment arm.

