Previous literature suggests that participants are sensitive to stimulation until the sensory neurons in the skin acclimate to the stimulation. Thus, we will use sham stimulation as an active control condition. We will inform our participants that they will sense the stimulation in the skin but will acclimate to the stimulation soon after it begins. They will be informed that they will receive two version of the stimulation, to facilitate blinding in case the participant does not acclimate to the stimulation. For sham, a genuine cross-frequency waveform will be delivered at maximum strength for 12 s, followed by a ramp-down. The ramp-up and ramp-down during the sham stimulation is designed to mimic the feeling of acclimation that is experienced with verum stimulation due to sensory adaptation. Published data from Consultant [name]'s lab indicate that this procedure provides sufficient participant blinding to the condition⁴.

6) Cognitive Control Task (Emotion Go-NoGo Task)

Participants will engage in an Emotion Go-NoGo task to activate affective cognitive control during the baseline EEG as well as the stimulation sessions. In this task, participants view facial images exhibiting different emotions (neutral, happy, sad, or angry). For each face (150 ms), they are to press a button within 1500 ms if the face expresses the target emotion (Go trials; 80%) and withhold the response if the face expresses the distractor emotion (NoGo trials; 20%); the pairing of target and distractor emotions vary across blocks. The task includes a total of 640 trials, divided into 8 blocks of 80 trials each. Half (4) of the blocks include original face images (Easy condition), and the other half (4) include visually degraded images (Difficult condition). The two difficulty conditions are presented in alternating order (counter-balanced across participants). Accuracy (particularly on NoGo trials) and reaction time (on Go trials) will be used to index cognitive control behavior as outcome measures. [*Note: the timing and trial parameters of the actual task may be modified slightly depending on initial testing results].

- 7) *Stimulation Side Effects Questionnaire*. Participants will complete this questionnaire regarding their experience following each stimulation session. They will also be asked to rate how much the stimulation improved cognitive performance as well as if they experienced any side effects (e.g., headache, neck pain, tingling).

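### The Aim 2 cross-over model has no period (Session 2 versus 3) term; adding one is a cheap improvement, and the stated power stands

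*Combined protocol and SAP*

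**What the plan says.** Section 2.0 sets the design: "The randomized, double-blind, sham-controlled, cross-over study will involve three sessions". Under Randomization, section 5.2 fixes two sequences: "If participants are randomized to the active group at Session 2, they will go to the sham group at Session 3, and vice versa". It adds that "The randomization schedule will ensure an equal distribution across the group". Sessions 2 and 3 are about a week apart, and "Procedures will be identical for each session". On the task, section 5.2 says: "Participants will engage in an Emotion Go-NoGo task to activate affective cognitive control during the baseline EEG as well as the stimulation sessions".

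For Aim 2, section 7.0 says that rest-block PAC, d', β and reaction time "will be analyzed in separate repeated-measures ANCOVAs, with stimulation (tACS, sham) as within-subjects factor". The covariates implied by ANCOVA are not named, and the Statistical Power paragraph calls the same models ANOVAs. That paragraph also plans an analysis of sex and a Bayesian analysis taken from a cited publication. Neither is described with a period term, and no other section supplies one.

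On attrition, section 7.0 puts the "average dropout rate for each subsequent session is 10-15" per cent and says: "We will enroll 30 participants to ensure that at least 20 participants will complete the study even with an overall dropout of 30" per cent.

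**The concern.** In a two-by-two cross-over each participant's tACS minus sham difference contains the stimulation effect plus or minus any change between Session 2 and Session 3, with the sign set by sequence. Practice, familiarity with the set-up or fatigue could produce such a change. A model with stimulation alone does not separate it. Two consequences follow.

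- With equal numbers completing each sequence, the shift cancels from the mean but adds to the spread of the differences. The interval is wider than it need be and the test is conservative.
- With unequal numbers, part of the shift also enters the estimate, in either direction.

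A participant-level covariate entered only as a main effect does not help, because it does not vary between the two sessions. The loss matters because section 7.0 presents effect size estimates for later trials as a main product of this small study.

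**Working it through.** **Inputs from section 7.0.** N = 20 completers, within-subject correlation ρ = 0.8, f = 0.21, alpha 0.05, stated power 80%; 30 enrolled, 10-15% dropout per later session, 30% overall. Section 5.2 gives 1:1 allocation to sequence.

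**Assumption.** The shift (Session 3 minus Session 2 mean) is not in the documents. It is shown at 0.1, 0.2 and 0.25 of the single-session SD.

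**1. The plan's own figure.** For two levels, λ = f² × N × 2/(1−ρ) = 0.0441 × 20 × 2/0.2 = 8.82 on (1, 19) df. Power is 0.804, so the stated 80% reproduces. Equivalently, the target difference is 2 × 0.21 = 0.42 SD and the SD of the paired difference is √(2 × (1−0.8)) = 0.632.

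**2. Cost of a period term if there is no shift.** The adjusted estimate is the average of the two sequence means of the differences, with variance 0.4 × (1/n1 + 1/n2)/4 on N−2 df. The unadjusted variance is 0.4/N on N−1 df.

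| Completers | Power without | Power with |
|---|---|---|
| 10:10 | 0.804 | 0.802 |
| 11:9 | 0.804 | 0.798 |
| 12:8 | 0.804 | 0.786 |
| 13:7 | 0.804 | 0.764 |
| 11:11 | 0.844 | 0.842 |
| 13:9 | 0.844 | 0.830 |
| 12:12 | 0.876 | 0.875 |
| 14:10 | 0.876 | 0.865 |

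**3. Balanced completers (10:10) with a shift.** These figures are simulated, with at least 400,000 trials per cell. They compare a one-sample t test on the differences (the plan) with the period-adjusted two-sequence t test.

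| Shift (SD) | Power without / with | Mean 95% CI width without / with (SD) | Type I error without |
|---|---|---|---|
| 0.1 | 0.80 / 0.80 | 0.59 / 0.59 | 4.7% |
| 0.2 | 0.77 / 0.80 | 0.61 / 0.59 | 4.0% |
| 0.25 | 0.76 / 0.80 | 0.63 / 0.59 | about 3.5% |

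An extreme 0.5 SD shift, larger than the target effect, gives power 0.61 without the term. The variance of the differences is inflated by 1 + shift² × (20/19)/0.40, which is 1.026, 1.105 and 1.164 at the three shifts.

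**4. Completers implied by per-session dropout.** 30 × 0.85² = 21.7 and 30 × 0.9² = 24.3. At 11:11, power without the term is 0.84 / 0.82 / 0.80, against 0.84 with it. At 12:12 it is 0.87 / 0.85 / 0.84, against 0.87.

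**5. Unequal completers (12:8).** Bias = shift × (12−8)/20. The unadjusted mean squared error is 0.4/20 + bias². The adjusted one is 0.4 × (1/12 + 1/8)/4 = 0.0208.

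| Shift (SD) | Bias (SD), share of 0.42 | Power if shift is against / for tACS | MSE without / with |
|---|---|---|---|
| 0.1 | 0.02, 5% | 0.76 / 0.83 | 0.0204 / 0.0208 |
| 0.2 | 0.04, 10% | 0.69 / 0.85 | 0.0216 / 0.0208 |
| 0.25 | 0.05, 12% | 0.645 / 0.85 | 0.0225 / 0.0208 |

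Adjusted power is 0.79 throughout. Unadjusted type I error stays below 5% at 12:8. At 13:7 it is 5.2, 5.7 and 6.1%.

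**6. Break-even.** Adjustment lowers mean squared error when the shift exceeds √(Var_adj − Var_unadj) / (|n1−n2|/N). That is 0.142 to 0.148 SD at N = 20 and 0.130 to 0.137 SD at N = 22 to 24.

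**7. How likely is imbalance?** Take 15 per sequence and independent completion with probability 0.81, 0.7225 or 0.70. A gap of 4 or more then has probability 10.0, 15.1 or 16.1%, and a gap of 6 or more 1.0, 2.4 or 2.7%. If exactly 20 of 30 complete (hypergeometric), the figures are 24.5% and 5.0%.

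**The case against.** The strongest reply is that the design already does most of the work. Order is randomised with equal allocation, so with balanced completers the planned estimate is unbiased and its type I error does not exceed 5%. First exposure to the task is at Session 1, outside the contrast, and PAC is measured at rest. No shift is documented. With 22 to 24 balanced completers, power stays at 0.80 or above for every shift up to 0.25 SD. With unequal completers, adjustment increases mean squared error if the shift is below about 0.14 SD. All of this stands, and it makes the point an improvement and not a defect that invalidates the test.

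A second reply is that ANCOVA without named covariates leaves period unspecified, not excluded. If sequence were entered with its interaction with stimulation, that interaction would be the period effect. This is true, but the documents do not say so, and the planned sex analysis does not supply the term. The source for the Bayesian model was not available to check. An unspecified term is itself a reason to write it down, so that the choice between adjusted and unadjusted results is not made after the data are seen.

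A third reply is that the harm to later sample sizes is an inference: section 7.0 mentions effect size estimates only. That is right. The 11 to 16% inflation at 0.2 to 0.25 SD applies only if the SD of the paired differences is used to size another cross-over, and at 0.1 SD it is about 3%.

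**Conclusion.** The concern holds: no model for the four Aim 2 primary outcomes contains a period term, although the design is a two-period cross-over. Confidence is high on the omission and the arithmetic, and does not extend to the size of any shift. For assumed shifts up to 0.25 SD, the loss with 20 balanced completers is at most about 4 points of power (0.76 against 0.80) and an interval of 0.63 against 0.59 SD. At 12:8 there is also a bias of up to 12% of the target effect, in a direction that cannot be known beforehand. Type I error above 5% appears only at a split as uneven as 13:7, and a gap of 6 or more has a 1 to 5% chance. The power statement is correct and N = 20 still gives 80% with the term. This should be fixed because it is standard for the design and nearly free.

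**What to change.** Before analysis, add to section 7.0 for each Aim 2 outcome:

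> The tACS minus sham difference will be estimated in a linear mixed model with fixed effects for stimulation, period (Session 2 vs 3) and sequence, and a random participant effect, and reported with its 95% CI.

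The period-adjusted two-sequence t test on completers would also do. It is the analysis evaluated above and matches the mixed model when all pairs are complete. Name any further covariates in the same place. The period term does the work; a sequence main effect alone does not, and neither term corrects carry-over.

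The change is wording only, with no effect on design or enrolment. It costs one error degree of freedom when completers are balanced. If there is no shift and completers are unequal at N = 20, it costs about 2 points of power at 12:8 and 4 at 13:7. The 0.14 SD break-even should be accepted knowingly: below it, with unequal completers, the adjusted estimate is slightly less precise overall.

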- 4) *Self-Rated Assessments*. Participants will fill out BDI, ASRM, and PSWQ questionnaires. Any additional questionnaires not completed at the previous visit may be completed at this time or given to the participants to complete at home.
- 5) EEG and brain stimulation. EEG procedures will be repeated from Session 1. CF (cross frequency)-tACS targeting theta-gamma PAC will be administered in accordance to Consultant [name]'s published protocol⁴, which has successfully enhanced theta-gamma PAC and cognitive control in non-psychiatric individuals. Participants will be fitted using a montage consisting of 9 electrodes placed over the left frontal scalp.

Soterix Medical High-Definition Transcranial Alternating Current Stimulation device (HD-tACS) will be used to deliver current to the electrodes to generate tACS resembling theta-gamma PAC^{4,10,11}. The impedance of each stimulation electrode will be kept below 10 k Ω . The stimulation waveform will consist of a theta component (5 Hz) delivered at 0.96 mA (1.92 mA peak-to-peak) delivered in a constant sine wave and a gamma component (50 Hz), 3.5 cycles of a sine wave delivered at 0.64 mA (1.28 mA peak-to-peak) superimposed on the theta component and centered on the peak of each cycle. For both tACS and sham conditions, the stimulation will slowly ramp up over the course of 12 s, then the task will begin soon after maximum stimulation output is reached. Stimulation will be maintained at a stable level until the task is complete and the stimulation will ramp down over 12 s. Actual parameters may be varied slightly, but not enough to affect the risk to the participants.

tACS Study (HUM00208557)

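### The Aim 2 repeated-measures ANCOVA leaves out participants with only one stimulation session: little precision is lost, but dropout that differs by sequence would bias the tACS-sham contrast

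*Combined protocol and SAP*

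**What the plan says.** Section 7.0 (Aim 2) puts theta-gamma PAC, d', response bias and Go reaction time into "separate repeated-measures ANCOVAs, with stimulation (tACS, sham) as within-subjects factor". It names no covariate, period term, sequence term, analysis set or missing-data method. The power paragraph of the same section describes the tests as ANOVAs ("For the repeated-measures ANOVAs in Aim 2"). It states that "a sample size of 20 would provide 80% power at alpha level of .05" to "detect small-to-medium within-subjects effect sizes of f=0.21", with a within-subject correlation of 0.8.

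Dropout is dealt with only through enrolment. The plan expects that "average dropout rate for each subsequent session is 10-15" per cent, and enrols 30 so that at least 20 complete after an overall loss of 30%. A complete-pair analysis is therefore implied, though never stated.

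Section 2.0 makes withdrawal during or after a stimulation session a primary outcome of Aim 1, and Section 7.0 compares discontinuation between tACS and sham. The stopping rules in Section 5.2 end a session for intolerable discomfort and let the investigator withdraw a participant whose symptoms worsen. Section 8.4 allows the data of someone who leaves after enrolment to be destroyed if that person wishes.

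**The concern.** In a two-level repeated-measures model each person contributes the tACS-minus-sham difference. Someone stimulated at Session 2 who does not return has no difference and disappears from Aim 2, although a valid measurement was taken under a randomised condition.

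Two things could be lost. One is information. The other is the balance between the sequences. If people leave after Session 2 because of how that session went, and this happens more after active than after sham stimulation, the active-first participants who remain are a selected group. The plan treats differential withdrawal as possible, since it sets out to measure it. It also intends the Aim 2 estimates to feed the sample sizes of later trials, so a shift in the estimate would be carried forward.

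**Working it through.** **Inputs.** From Section 7.0: N = 20 completers, f = 0.21, correlation ρ = 0.8, alpha 0.05, 30 enrolled, dropout 10-15% per session. From Section 5.2: 1:1 allocation to sequence. Assumptions made here: ρ = 0.5 as a less favourable value, the dropout patterns in step 3, and the practice effect in step 5.

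**1. The plan's power.** For a two-level within-subject factor, λ = N × 2 × f² / (1 − ρ) = 20 × 2 × 0.0441 / 0.2 = 8.82. With 1 and 19 df the power is 80.4%, so the stated 80% reproduces. For two levels the effect is 2f = 0.42 between-person SD.

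**2. How many people have Session 2 only.** Apply the per-session rate before Session 2 and again before Session 3.

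| Dropout per session | Reach Session 2 | Complete | Session 2 only |
|---|---|---|---|
| 10% | 30 × 0.90 = 27 | 27 × 0.90 = 24.3 | 2.7 |
| 15% | 30 × 0.85 = 25.5 | 25.5 × 0.85 = 21.7 | 3.8 |

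**3. Bias of the complete-pair estimate.** Suppose the lowest-scoring 15% of active-first participants leave after Session 2, taking a higher score as better. Those who stay have a Session 2 mean raised by φ(z)/(1 − 0.15) = 0.274 SD, where z is the 15th percentile of the standard normal. Their Session 3 mean is raised by ρ × 0.274. The tACS-sham difference in that sequence is therefore too large by 0.274 × (1 − ρ). With each sequence weighted equally, half of this enters the estimate.

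- ρ = 0.8: 0.274 × 0.2 / 2 = +0.027 SD; 0.027 / 0.42 is about 6%.
- ρ = 0.5: 0.274 × 0.5 / 2 = +0.069 SD; 0.069 / 0.42 is about 16%.

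Weighting people equally gives slightly less: 0.0549 × 0.85 / 1.85 = +0.025 SD at ρ = 0.8. The standard error of the contrast at N = 20 and ρ = 0.8 is √(2 × 0.2 / 20) = 0.141 SD, so the bias is about 0.19 of a standard error.

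Other patterns at ρ = 0.8:

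- Random loss, or the same rule in both sequences: about zero, because the two shifts cancel.
- The two sequences selected in opposite directions, 15% each: 0.274 × 0.2 = +0.055 SD (13%).

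**4. Precision.** Take nc completers and k people seen at Session 2 only. A model with stimulation and period, using all sessions, has efficiency 1 + (k/nc)(1 − ρ)/2 relative to complete pairs.

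- 10% dropout: 1 + (2.7/24.3) × 0.1 = 1.011.
- 15% dropout: 1 + (3.825/21.675) × 0.1 = 1.018.
- 20 completers and 4 singles: 1 + (4/20) × 0.1 = 1.020.

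Adding a sequence term trims this slightly. For 20 and 4 it becomes (0.4/20) / (0.04/24 + 0.36/20) = 1.017. With one df given to period, power goes from 80.4% to 80.8%.

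**5. Does the alternative remove the bias?** In simulations with 26 people reaching Session 2 and the correlation treated as known, a likelihood model using all sessions with a period term stayed within 0.005 SD of zero under the selection patterns examined. The period term matters. With a 0.3 SD practice effect and loss in the active-first sequence only, the all-session model without it kept about +0.02 SD of bias.

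**The case against.** The strongest reply is that the plan has already allowed for this. It enrols 30, expects 30 × 0.7 = 21 completers and computes power on 20, so stated power does not depend on single-session participants. The bias needs loss that depends on the outcome and differs by sequence. Even then it is about a fifth of a standard error at the plan's correlation. Withdrawal is reported as an outcome, so differential loss would be seen. Aim 2 is preliminary estimation, and a Bayesian analysis is planned beside the ANCOVA.

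Most of this stands, and it limits the size of the point. Enrolling more people restores the number of pairs but does not undo a selection of who remains. Reporting withdrawal shows the problem without correcting the estimate. The Bayesian analysis cites a hierarchical-modelling tutorial, but the plan does not give its model or say what it does with incomplete pairs.

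A reader might go further and infer that the ANCOVA wastes the session-level mood scores, and that adjusting for them would raise power. Section 5.2 lists them before the stimulation step ("In-person clinical assessments will be completed by a trained member of staff"; "Participants will fill out BDI, ASRM, and PSWQ questionnaires"). The documents do not support that inference:

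- With two sessions, the outcome difference can be regressed on the mood difference, so the scores are not out of reach.
- No correlation between mood change and any Aim 2 outcome is given.
- Session 3 mood is measured after Session 2 stimulation and could carry its effect.
- The adjustment has a price. In a paired-difference regression at N = 20, power falls from 80.4% to about 78% with one uninformative covariate and about 75% with two, because chance mood differences add variance.

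Mood adjustment is a trade-off and not a defect in the plan.

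**Conclusion.** The point holds in a limited form. The Aim 2 model as named excludes about 3 to 4 of 30 participants at the plan's own dropout rate, and no missing-data rule says otherwise. The precision cost is minor: 1-2% of information at ρ = 0.8, under one power point.

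The reason to change is protection against bias. Under one-sided, outcome-related loss of 15% in the active-first sequence, the bias is about +0.03 SD (6% of the planned effect) at ρ = 0.8 and about +0.07 SD at ρ = 0.5. It is near zero if loss is random or symmetric. These figures rest on assumed dropout patterns. The documents do not show that such loss will occur, only that they treat withdrawal as something that may differ between tACS and sham. It would be wrong to conclude that the planned analysis is underpowered or seriously biased.

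**What to change.** Replace the Aim 2 ANCOVAs with one linear mixed model per outcome (REML, Kenward-Roger degrees of freedom). Fit stimulation, period and sequence as fixed effects and a participant random intercept. Include every stimulated session with usable data, and define in advance what makes a partly completed session usable. Keep the complete-pair analysis as a sensitivity analysis, and use the same model name in the power paragraph.

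With these terms each of the four sequence-by-session means is free, so loss that depends on the observed Session 2 result, even differently by sequence, is accommodated under missing at random.

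The cost is SAP wording, slightly more analysis work and one degree of freedom for period (at N = 20 complete pairs, 80.4% becomes 80.2%). No new data or visits are needed. The model cannot help where a session gave no usable outcome, or where data are destroyed at a participant's request under Section 8.4. The number of such cases should be reported by sequence.
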